7.2. Efficacy Data

For binary variables, such as ACR20, remission with respect to $SDAI \leq 3.3$, if the value is missing due to missing values in any of the components, while the subject is still enrolled, the method of last observation carried forward (LOCF) will be used to carry forward any of the missing components, and from that mix of actual and carried forward values, the value of the binary composite variable will be determined. Note that, this approach should result in the same value for ACR20, ACR50 and ACR70 if their components are partially available but can be used to determine the ACR values without imputation (see definition for ACR response rate in [Appendix 1.4](#)).

This type of LOCF method will be known as “LOCF mixed components”, since it is based on calculating the composite value based on a mixture of values at a visit and values carried forward from previous visits. It can be justified as an attempt to carry forward as little information as possible.

After LOCF imputation has been applied, the composite binary variable can be calculated from the imputed components.

If baseline data is missing, then the post-baseline value will be set to non-responder.

DAS28-4(CRP), CDAI and SDAI are derived variables based on multiple components. If any component is missing, the endpoint will be considered as missing. A Mixed Model for Repeated Measures (MMRM) will be used to analyze continuous endpoints with repeated measures without explicit imputation for missing values.

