7.5. Assessments of Disease Activity

Individual components for the following indicators of disease activity will be collected throughout the study as described in [Table 2](#).

Table 2. Disease Activity Indicators

Indicator	Definition/Calculation
DAS28-4 (CRP)	$\text{DAS28-CRP}(4) = 0.56 \cdot \sqrt{(\text{TJC28})} + 0.28 \cdot \sqrt{(\text{SJC28})} + 0.36 \cdot \ln(\text{CRP}+1) + 0.014 \cdot \text{PtGA} + 0.96$
Simplified Disease Activity Index (SDAI)	$(28\text{TJC}) + (28\text{SJC}) + \text{PhyGA} + \text{PtGA} + \text{CRP}$
Clinical Disease Activity Index (CDAI)	$(28\text{TJC}) + (28\text{SJC}) + \text{MDGA} + \text{PtGA}$
American College of Rheumatology (ACR) Response Rates	
The ACR’s definition for calculating a 20% improvement in RA (ACR20) is as follows: a 20% improvement in tender and swollen joint counts and 20% improvement in 3 of the 5 remaining ACR-core set measures: patient and physician global assessments, pain, disability, and an acute-phase reactant (eg, CRP). Similarly, ACR50, 70 and 90 are calculated with the respective percent improvements.

ACR/EULAR Boolean-based definition of remission	
At any time point, a subject must satisfy all of the following: tender joint count ≤ 1, swollen joint count ≤ 1, CRP ≤ 1 mg/dL, patient’s global assessment of health ≤ 1 on a 0-10 scale

TJC = tender joint count; SJC = swollen joint count; CRP = C-reactive protein in mg/L; PtGA = patient’s global assessment of health; PhyGA = physician’s global assessment of health

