6. ENDPOINTS AND COVARIATES

6.1. Efficacy Endpoints

Efficacy endpoints will be secondary endpoints in this safety study. The efficacy endpoints are:

- *Change from baseline to each post-baseline scheduled visit in DAS28-4 (CRP), Simplified Disease Activity Index (SDAI) and Clinical Disease Activity Index (CDAI).*
- *Rate of remission at each post-baseline scheduled visit including:*
 - *ACR-EULAR Boolean remission (defined as the subject satisfying all of the following: tender joint count ≤ 1 , swollen joint count ≤ 1 , C-reactive protein ≤ 1 mg/dl, patient global assessment ≤ 1 on a 0-10 scale);*
 - *SDAI ≤ 3.3 ;*
 - *CDAI ≤ 2.8 .*
- *Rate of low disease activity (LDA) at each post-baseline scheduled visit including:*
 - *SDAI ≤ 11 ;*
 - *CDAI ≤ 10 ;*
 - *Disease Activity Score (DAS)28-4(CRP) ≤ 3.2 .*
- *ACR20, ACR50, and ACR70 response rate of at each post-baseline scheduled visit.*
- *Change from baseline to each post-baseline scheduled visit in the HAQ-DI.*

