8.2.3. Analyses of Efficacy Endpoints

All efficacy analyses will be based on the Full Analysis Set.

Descriptive statistics of efficacy endpoints for all subjects in the study will be provided from baseline to the declared end of the study. Differences between each tofacitinib regimen (5 mg BID, 10 mg BID, or combined) and the TNFi regimen as well as between tofacitinib regimens will be estimated. The difference estimates will be derived based on the following models:

- Analysis of continuous data, ie, change from baseline in DAS28-4(CRP), SDAI, CDAI, HAQ-DI will be analyzed using 95% CI of treatment difference based on MMRM analysis. (See discussions in [Section 8.1.3](#)).
- Dichotomized data will be summarized and compared between treatment groups using the normal approximation of binomial proportions and 95% CI of treatment difference (see discussions in [Section 8.1.4](#)). This approach will be used for the following efficacy variables:
 - Rate of remission: ACR-EULAR Boolean remission, SDAI ≤ 3.3 , CDAI ≤ 2.8 .
 - Rate of low disease activity (LDA): SDAI ≤ 11 , CDAI ≤ 10 , DAS28-4 (CRP) ≤ 3.2 .
 - ACR20, ACR50, and ACR70 response rate.

For efficacy analyses, the treatment groups will be tofacitinib 5 mg BID, tofacitinib 10 mg BID, and TNFi regimen.

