Appendix 1.4. Further Definition of Endpoints

Indicator	Definition/Calculation
DAS28-4 (CRP)	$DAS28-4(CRP) = 0.56 * \sqrt{TJC28} + 0.28 * \sqrt{SJC28} + 0.36 * \ln(CRP+1) + 0.014 * PtGA + 0.96$
Simplified Disease Activity Index (SDAI)	$(TJC28) + (SJC28) + PhyGA/10 + PtGA/10 + CRP/10$
Clinical Disease Activity Index (CDAI)	$(TJC28) + (SJC28) + PhyGA/10 + PtGA/10$
American College of Rheumatology (ACR) Response Rates	The ACR’s definition for calculating a 20% improvement in RA (ACR20) is as follows: a 20% improvement in tender and swollen joint counts and 20% improvement in 3 of the 5 remaining ACR-core set measures: patient and physician global assessments, pain, disability, and an acute-phase reactant (eg, CRP). Similarly, ACR50, 70 and 90 are calculated with the respective percent improvements.
ACR/EULAR Boolean-based definition of remission	subject must satisfy all of the following: $TJC28 \leq 1, SJC28 \leq 1, CRP \leq 10, PtGA \leq 10$

where TJC28 is number of painful joints out of 28 joints; SJC28 is number of swollen joints out of 28 joints; PtGA is the patient’s global assessment of disease activity on a 100 mm VAS; PhyGA is the physician’s global assessment of disease activity on a 100 mm VAS; CRP = C-reactive protein in mg/L; ln is the natural logarithm; sqrt is square root

Patient’s Global Assessment of Health: Subjects will answer the following question, “Considering all the ways your arthritis affects you, how are you feeling today?” The subject’s response will be recorded using a 100 mm visual analog scale (VAS).

Physician’s Global Assessment of Health: The investigator will assess how the subject’s overall arthritis appears at the time of the visit. This is an evaluation based on the subject’s disease signs, functional capacity and physical examination, and should be independent of the Patient’s Global Assessment of Arthritis. The investigator’s response will be recorded using a 100 mm visual analog scale (VAS).

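### As written, the missing-baseline rule in SAP 7.2 also turns an observed remission or low disease activity into non-response, though neither endpoint uses a baseline

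*SAP*

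**What the plan says.** SAP 7.2 opens its missing-data rules with "For binary variables, such as ACR20, remission with respect to" SDAI of 3.3 or below. It fills missing components by LOCF while the subject is still enrolled, and continues: "After LOCF imputation has been applied, the composite binary variable can be calculated from the imputed components". The next sentence is the rule at issue: "If baseline data is missing, then the post-baseline value will be set to non-responder". The text then moves to the continuous scores. Nothing in the section limits the rule to particular binary endpoints or says what counts as missing baseline data.

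SAP 6.1 and 8.2.3 list nine binary efficacy endpoints:

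- Three remission endpoints (Boolean, SDAI, CDAI), introduced in 6.1 as "Rate of remission at each post-baseline scheduled visit including" those criteria.
- Three LDA endpoints, which 8.2.3 begins with "Rate of low disease activity (LDA): SDAI" and follows with CDAI and DAS28-4(CRP).
- ACR20, ACR50 and ACR70 response.

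**The concern.** A missing baseline makes ACR response impossible to compute, so some convention is needed there, and scoring the subject as a non-responder is a common one. Remission and LDA are different: they can be computed in full without any baseline. For those endpoints the rule replaces an outcome that was seen with one known to be wrong, and repeats this at every visit for that subject.

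At stake is the accuracy of six secondary efficacy rates and the differences between arms estimated from them. The co-primary safety endpoints, MACE and malignancy, are not touched.

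**Working it through.** The documents state no figure for this rule: no missing-baseline rate and no expected remission or LDA rate. There is therefore nothing to reproduce. The check sets the text side by side and then does simple arithmetic on assumed values.

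**Which endpoints need a baseline**

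| Endpoint | Definition | Baseline needed? |
|---|---|---|
| ACR20/50/70 | Percent improvement; for ACR20, "a 20% improvement in tender and swollen joint counts" plus three of five other measures (SAP Appendix 1.4) | Yes |
| Boolean remission | "subject must satisfy all of the following": same-visit limits on joint counts, CRP and patient global (SAP Appendix 1.4); Protocol 7.5 says "At any time point, a subject must satisfy all of the following" | No |
| SDAI ≤3.3, CDAI ≤2.8 | Sum of same-visit components | No |
| LDA: SDAI ≤11, CDAI ≤10, DAS28-4(CRP) ≤3.2 | Same-visit score | No |

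Six of the nine binary endpoints use no baseline value.

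**Whether another provision removes the case**

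- The Full Analysis Set (SAP 5.1) requires randomization and one dose, not a baseline. These subjects stay in the analysis.
- The repeated-measures model for continuous endpoints (SAP 8.1.3) excludes a subject without a baseline. The same person would be left out of change in CDAI but counted as a failure for CDAI remission.
- SAP Appendix 1.1 lets a labeled baseline visit dated up to 30 days before dosing (40 days for laboratory values) serve as baseline. This rescues visits with an off-target date, not items that were never recorded. The schedule of activities first collects the patient and physician global assessments at Visit 1, so no scheduled screening value can stand in. Patient global enters all six endpoints; physician global enters the four based on SDAI or CDAI.

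**Size, under independence**

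Let m be the share of subjects at a visit who lack baseline, and p the true rate. If m is unrelated to outcome:

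- Reported rate = p(1−m), so bias = −p × m.
- Subjects recoded per arm = 1300 × p × m (about 1300 per arm, SAP 2.1).

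| m (assumed) | p (assumed) | Bias, points | Recoded of 1300 |
|---|---|---|---|
| 0.5% | 15% | −0.08 (0.075) | 1.0 |
| 1% | 30% | −0.3 | 3.9 |
| 2% | 50% | −1.0 | 13.0 |
| 5% | 50% | −2.5 | 32.5 |

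Without independence, bias = −m × (true rate among those lacking baseline). That lies between 0 and −m points: at m = 1%, between 0 and −1 point.

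**Difference between arms**

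- Equal m: reported difference = (p1 − p2)(1−m).
- Unequal m, same p in both arms: spurious difference of size p × |m1 − m2|. At p = 50% with 1% against 3%, this is 0.5 × 2 = 1.0 point.
- How far m could differ by chance: with m = 2% in both arms of 1300, the standard deviation of the difference in m is √(2 × 0.02 × 0.98 / 1300) = 0.55 points. A 1.96-SD gap is about 1.1 points, which at p = 50% gives 0.5 × 1.1 ≈ 0.5 points. The 1% against 3% example is 2/0.55 ≈ 3.6 SDs, so it is well beyond ordinary chance.
- For scale, the 95% CI half-width for a difference, 1.96 × √(2p(1−p)/1300), is 2.75 points at p = 15%, 3.52 at 30% and 3.84 at 50%.

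**The case against.** The strongest reply is that the authors may have meant ACR only. The SAP uses the word response for ACR20/50/70 and speaks of rates of remission and of low disease activity, so non-responder is ACR language. The same block also contains a note that concerns ACR alone. A reader might infer that the SAP deliberately scores every binary endpoint this way; the documents do not establish that intent. What they do establish is that the sentence carries no limit and sits in a block that names SDAI remission among its examples. A programmer following the text would apply it there.

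A second reply concerns bias between arms. A reader might infer that the rule favors one arm. Protocol 6.3 lists the baseline assessments ahead of the step that randomizes and dispenses drug, so missingness should differ between arms only by chance. That reply stands.

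A third is that counting incomplete subjects as non-responders is conservative and keeps one denominator. That is a reasonable defense where the outcome is unknown. It does not cover an outcome that was observed.

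Finally, baseline data should rarely be missing, efficacy is secondary, and the decision rules in SAP 4.2 concern only malignancy and MACE. All of this stands and limits the importance of the point.

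**Conclusion.** The point holds as a defect of wording with a small effect. Followed literally, SAP 7.2 records an observed remission or LDA as failure for any subject without baseline data, on six endpoints that need none. An ACR-only intent is possible but is not stated.

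Under independence, rates in all arms fall, by about 0.08 to 2.5 points over the assumed ranges of m and p. The upper end needs 5% missing baseline and a 50% rate, and nothing in the documents suggests either value. It would be tempting to say that each 1% of missing baseline lowers a rate by at most 1% of its value. That is the expected loss under independence, not a ceiling. Differences between arms are barely affected when m is similar, and a systematic advantage for one arm is not supported. No safety conclusion depends on this.

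**What to change.** Amend SAP 7.2 in three respects:

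1. Limit the missing-baseline sentence to ACR20, ACR50 and ACR70.
2. State what counts as missing baseline data: any one required component, or only a set that leaves the ACR response undeterminable.
3. State that remission and LDA are scored from the post-baseline components, under the same mixed-components LOCF rule as for all other subjects, whether or not a baseline exists. Saying only that observed values are used would give subjects without a baseline a different missing-data rule from everyone else.

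The cost is a few lines of SAP text and the matching program specification. No new data are needed. If ACR only was always meant, the change simply records it.

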7.3. Missing Data due to COVID-19 Pandemic

Because of the COVID-19 pandemic, some scheduled on-site visits may be substituted by remote visits such as telephone contacts. The data collected via the remote visits will be treated the same as the data collected by the on-site visits.

Missing data due to COVID-19 pandemic will be handled the same as that for other missing data.

In addition, the following summaries will be provided.

- Discontinuation due to COVID-19 impact will be reported in the disposition table.
- Missed visits due to COVID-19 impact are recorded as PD and will be in the specific PD tables in the Clinical Study Report (CSR).
- A set of summary/listing tables based on a subset of protocol deviations associated with COVID-19 will be provided. Study drug discontinuation, subject discontinuation due to COVID-19 and adverse events related to COVID-19 will be summarized as well. The source information will be captured in the protocol deviation.

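### SAP 7.2 scores remission and low-disease-activity cut-offs on components carried forward with no limit on age, while the continuous index at the same visit is left missing for the MMRM; impute the missing components instead and keep LOCF as a sensitivity analysis

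*SAP*

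**What the plan says.** SAP 7.2 opens with the binary rule: "For binary variables, such as ACR20, remission with respect to" SDAI ≤ 3.3 (ACR20 and this cut-off are the only two named), a value missing because of its components is rebuilt by LOCF. The condition is enrolment: "while the subject is still enrolled, the method of last observation carried forward (LOCF) will be used". The SAP calls this 'LOCF mixed components', describes it as based on "a mixture of values at a visit and values carried forward from previous visits", and gives a reason: "It can be justified as an attempt to carry forward as little information as possible". Then "After LOCF imputation has been applied, the composite binary variable can be calculated from the imputed components".

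The last paragraph of the same section turns to DAS28-4(CRP), CDAI and SDAI as derived variables: "If any component is missing, the endpoint will be considered as missing". The next sentence reads: "A Mixed Model for Repeated Measures (MMRM) will be used to analyze continuous endpoints with repeated measures without explicit imputation for missing values".

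SAP 8.2.3 reports both forms of all three indices: mean change by MMRM, and rates for SDAI ≤ 3.3 and ≤ 11, CDAI ≤ 2.8 and ≤ 10, and DAS28-4(CRP) ≤ 3.2. SAP 8.1.4 gives the rates a normal-approximation binomial interval. SAP 7.3 notes that "some scheduled on-site visits may be substituted by remote visits such as telephone contacts" and sends pandemic-related missing data through the same rules.

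**The concern.** A subject-visit with one missing component has no SDAI in the mean-change table but an SDAI class in the remission and low-disease-activity tables. The first relies on a missing-at-random assumption; the second assumes that nothing has changed since the component was last measured.

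Three features make the second assumption weak here:

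- **No age limit.** SAP 7.2 sets no maximum number of visits or days, no rule on whether baseline may be carried, and no rule for a wholly missed visit.
- **Treatment changes.** Under Protocol 5.6.1 and 6.2, subjects who stop study drug stay in the study. Nothing prevents a value recorded on randomized drug from being carried past a switch to standard of care, or a value from the 10 mg BID arm past the 2019 dose reduction described in SAP 8.2.
- **Telephone visits.** Joint counts need pressure or motion on the joint (Protocol 7.6.1), the physician global draws on physical examination (Protocol 7.9), and CRP is a central-laboratory test (Protocol 7.9.5). A telephone call alone supplies none of them.

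At stake are the secondary response rates and their intervals, and whether they agree with the mean changes in the same indices.

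**Working it through.** The plan gives no missingness rate and no figure on this point, so there is nothing of its own to reproduce. The values below marked as assumed are illustrations.

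**1. How old a carried value can be.** Target days from SAP Appendix 1.1, with visits 90 days apart:
- Month 12 to Month 36: 1080 − 360 = 720 days, or 720/90 = 8 visits.
- Month 12 to Month 60: 1800 − 360 = 1440 days, or 16 visits.

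**2. One subject.** Formulas from SAP Appendix 1.4: CDAI = TJC28 + SJC28 + PhyGA/10 + PtGA/10; SDAI adds CRP/10; DAS28-4(CRP) = 0.56√TJC28 + 0.28√SJC28 + 0.36 ln(CRP + 1) + 0.014 PtGA + 0.96. Assumed values, in the order TJC, SJC, PhyGA, PtGA, CRP: Month 12 is 1, 1, 10, 15, 4; true Month 36 is 6, 4, 35, 40, 12.

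| Month 36 scored on | CDAI | SDAI | DAS28 | Low disease activity |
|---|---|---|---|---|
| true values | 6+4+3.5+4.0 = 17.5 | 18.7 | 4.38 | none |
| joint counts carried from Month 12 | 1+1+3.5+4.0 = 9.5 | 10.7 | 3.28 | CDAI and SDAI |
| only patient global current | 1+1+1.0+4.0 = 7.0 | 7.4 | 2.94 | all three |

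In the last two rows the MMRM treats all three indices as missing. This subject worsened, so LOCF overstates response; for an improving subject it understates it.

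**3. Size on a rate.** Simulation of 400,000 subjects. Assumed: mean SDAI 20, 17, 13, 12 and 11.5 at Months 2, 3, 6, 9 and 12; between-subject SD 6; visit SD 5. SDAI is split into TJC, SJC, PhyGA, PtGA and CRP with shares 0.33, 0.22, 0.18, 0.22 and 0.05, with independent normal visit noise. Month 2 is complete, and later visits are affected at random. Only the missing components are carried. The true rate of SDAI ≤ 11 is about 39.9% at Month 6 and 47.5% at Month 12.

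| Missing at affected visits | Visits affected | Shortfall at Month 6, points | Shortfall at Month 12, points |
|---|---|---|---|
| one component at random | 10% / 20% | 0.4 / 0.8 | 0.0 / 0.1 |
| both joint counts | 10% / 20% | 1.1 / 2.3 | 0.2 / 0.5 |
| all but patient global | 10% / 20% | 1.5 / 3.2 | 0.3 / 0.7 |
| whole index (upper bound) | 10% / 20% | 1.9 / 3.9 | 0.3 / 0.9 |

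With the mean held at 11.5 throughout and 20% of visits affected, the shortfall is below 0.1 point for either of the two middle patterns.

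**4. Scale.** The standard error of one arm's rate with 1,300 subjects is √(0.4 × 0.6/1300) = 1.36 points. The Month 6 range for the two middle patterns is therefore 1.1/1.36 = 0.8 to 3.2/1.36 = 2.4 standard errors.

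**5. Interval.** SAP 8.1.4 uses p(1 − p)/n for each arm, with no term for carried values, so they enter as if observed.

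**The case against.** The best defence is that the SAP is open about what it does. The sentence that makes an index missing leads directly into the MMRM rule, and the binary rule is stated separately, named and justified. A reader might infer that the SAP contradicts itself. It does not: the rules differ by endpoint type, although the sentence is not expressly limited to continuous endpoints and should be.

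Other tempting readings also go too far:

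- **Carry-forward without any limit.** It stops when enrolment stops; what is missing is a cap on visits or days.
- **Response rates generally resting on old joint counts.** Only visits with a missing component are affected, and that component may be CRP or a global assessment.
- **Carrying the whole index forward.** The SAP keeps the components observed at the visit, so the last table row is an upper bound and not an estimate of the SAP's rule.
- **Pandemic visits producing the Month 6 bias.** The Protocol's entry for Amendment 8 records enrolment as closed, and the SAP version of 13 May 2019 already incorporates that amendment. A subject randomized as late as that date would leave the Month 6 window (Day 225, SAP Appendix 1.1) in December 2019. Telephone visits therefore fall mainly on later visits, where mean activity has probably flattened.

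It also stands that a bias equal in all arms cancels in the between-arm differences that SAP 8.2.3 estimates, and that nothing in the documents shows unequal missingness. Equality cannot be presumed either: the trial is open-label, and the 2019 dose reduction touched one arm only.

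**Conclusion.** The point holds as a low-cost improvement to secondary endpoints. Uncapped LOCF of components gives a directional bias in remission and low-disease-activity rates at affected visits while disease activity is changing, can carry values across a change of treatment, and is followed by intervals that ignore the imputation. Coverage of the CDAI, DAS28 and low-disease-activity cut-offs is inferred, because SAP 7.2 introduces its two named endpoints only as examples.

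Under the assumed trajectory, with 10 to 20% of visits affected and joint counts or everything but the patient global missing, the Month 6 understatement is about 1.1 to 3.2 points. It is about 0.7 point or less at Month 12 and close to zero on a plateau. These figures depend on assumed means, SDs, component shares and missingness, none of which the documents supply. They describe one arm's rate; a between-arm difference is biased only if missingness or trajectory differs by arm. The co-primary MACE and malignancy analyses are not touched.

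**What to change.** In SAP 7.2:

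1. Limit the sentence that makes an index missing to the continuous endpoints, and name every binary endpoint that the component rule covers.
2. For enrolled subjects, multiply impute the missing components from treatment, baseline and other visits' values, keeping every component observed at the visit. Derive the index, apply the cut-off in each imputed data set, and combine. Treat the Boolean remission and ACR components the same way. This uses the missing-at-random assumption that the SAP already accepts for the MMRM. Because joint counts are bounded integers and CRP is skewed, the imputation method should respect those scales.
3. Keep 'LOCF mixed components' as a sensitivity analysis.
4. Report the share of imputed components by arm and visit, so that readers can see where it matters.

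The cost is SAP wording and modest extra programming, with no new data. Intervals will be slightly wider, reflecting uncertainty that the current ones leave out.
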